8.2.1.1. Suspected Unexpected Serious Adverse Reactions

Suspected unexpected serious adverse reactions (SUSARs) are serious events that are not listed in the IB and that the investigator identifies as related to study drug or procedure. United States 21 CFR 312.32 and European Union Clinical Trial Directive 2001/20/EC and the associated detailed guidances or national regulatory requirements in participating countries require the reporting of SUSARs. Lilly has procedures that will be followed for the recording and expedited reporting of SUSARs that are consistent with global regulations and the associated detailed guidances.

8.2.2. Adverse Events of Special Interest

Skin rash is considered an AESI. If a subject develops a rash during the study, the subject should notify the site immediately in order to conduct an unscheduled visit. The visit should be

scheduled as soon as possible to enable evaluation of the rash while it is still present. See Section 8.4.6 for instructions on rash assessment and management.

8.2.3. Complaint Handling

Lilly collects product complaints on IPs and drug delivery systems used in clinical studies in order to ensure the safety of study participants, monitor quality, and facilitate process and product improvements.

Subjects will be instructed to contact the investigator as soon as possible if they have a complaint or problem with the study drug so that the situation can be assessed.

8.3. Treatment of Overdose

In case of suspected overdose, subjects should be closely monitored for electrocardiogram (ECG) changes; clinical laboratory abnormalities (hematology and serum chemistry); and adverse skin reactions and any associated localized, generalized, and/or systemic symptoms, which may include skin irritation, rash, skin exfoliation, pruritus, urticaria, fever, edema, or joint pain/swelling. Investigators should remain vigilant for unknown effects related to LY3337641 overdose.

There is no known antidote for overdose of LY3337641.

8.4. Safety Assessments

8.4.1. Physical Examination

Complete physical examinations and symptom-directed physical examinations will be conducted as specified in the Schedule of Activities ([Appendix 2](#)) and as clinically indicated. A complete physical examination should include evaluation of the following regions/systems:

- general appearance
- skin
- head, ears, eyes, nose, throat
- lymph nodes
- cardiovascular
- respiratory
- abdominal
- genitourinary (only as clinically indicated)
- extremities (tender/swollen joint counts to be documented separately)
- neurologic

On visit days where a complete physical examination is not required, as detailed in the Schedule of Activities ([Appendix 2](#)), the investigator may conduct a symptom-directed physical examination as clinically indicated.

8.4.2. Vital Signs

Blood pressure and heart rate will be measured as specified in the Schedule of Activities ([Appendix 2](#)) and as clinically indicated. These should be measured after at least 5 minutes of sitting.

Unscheduled orthostatic vital signs should be assessed, if possible, during any AE of dizziness or posture-induced symptoms. If the subject feels unable to stand, sitting or supine vital signs should be recorded.

Additional vital signs may be measured during each study visit if warranted, as determined by the investigator.

Body temperature will be measured as specified in the Schedule of Activities ([Appendix 2](#)) and as clinically indicated.

Any clinically significant findings that occur after the subject receives the first dose of study drug should be reported to Lilly or its designee as an AE via the eCRF.

8.4.3. Electrocardiograms

For each subject, ECGs should be collected according to the Schedule of Activities ([Appendix 2](#)).

Subjects should lie supine for approximately 5 to 10 minutes before ECG collection and remain supine but awake during ECG collection. If possible, ECGs should be recorded prior to drawing blood and measuring blood pressure and pulse.

Electrocardiograms may be obtained at additional times when deemed clinically necessary. Collection of more ECGs than expected at a particular time point is allowed when needed to ensure high quality records.

Electrocardiograms will be locally interpreted by a qualified physician (the investigator or qualified designee) at the site as soon after the time of ECG collection as possible, and ideally while the subject is still present, to determine whether the subject meets entry criteria and for immediate subject management, should any clinically relevant findings be identified. The investigator (or qualified designee) must document the review of the ECG. All recorded ECGs should be stored at the site and made available to the sponsor as requested.

Any clinically significant findings from ECGs that result in a diagnosis and that occur after the subject receives the first dose of the study drug should be reported to Lilly or its designee as an AE via the eCRF.

8.4.4. Chest Radiography and Tuberculosis Testing

Posteroanterior and lateral chest radiography will be performed at screening for all subjects unless these have been obtained within 90 days prior to initial screening and the radiographs or report is available for investigator review. Variations on the chest radiography view requirements will only be permitted if the country/local guidelines of care for standard TB screening differ from these protocol specifications.

All subjects will undergo a TB test at screening (TST or interferon γ release test). Refer to Exclusion Criterion [21] for details regarding TB testing.

See Section 5.3 for subjects who are rescreening for this study and have undergone radiography and/or TB testing as part of their initial screening.

8.4.5. Laboratory Tests

For each subject, the laboratory tests detailed in Appendix 3 should be conducted according to the Schedule of Activities (Appendix 2).

Any clinically significant findings that occur after the subject receives the first dose of study drug should be reported to Lilly or its designee as an AE via the eCRF.

8.4.6. Assessment and Management of Subjects Developing a Rash

Subjects who develop a skin rash should be evaluated as soon as possible. Investigators will be prompted to categorize and diagnose the rash (per clinical judgment), assess relatedness to study drug, and grade severity according to Common Terminology Criteria for Adverse Events. This information will be entered into a form incorporated into the eCRF. Additional information related to the rash evaluation will also be entered into this form and will include a history of infections and allergies; and recent exposure to prescription or over-the-counter medications, skin products, detergents, or other potential skin irritants. A review of systems will be completed to assess for systemic symptoms and concurrent illnesses. A targeted physical examination should be performed, including an evaluation of the rash distribution and type, vital signs and temperature, and other organ systems, as clinically indicated. In addition, photographs and laboratory measurements should be obtained as clinically indicated, according to investigator judgment. The subject should be evaluated to determine whether there are any signs or symptoms suggesting a severe, potentially life-threatening condition.

If a subject develops a rash that is assessed as not related to study drug, is transient, or is not clinically significant in the opinion of the investigator, the study drug may be continued without interruption. In some cases, the investigator may instead choose to interrupt the study drug and restart it at a later date. The dates for stopping and restarting the study drug should be captured.

Immediate and permanent discontinuation of study drug should be considered for all subjects with clinically significant rash. For rashes deemed clinically significant, punch biopsy(ies) of the rash should also be performed. In addition, a venous blood sample should be collected for PK analysis at the time of evaluation with documentation of the date and time of administration of the most recent dose of study drug.

Subjects should be followed up until resolution of the rash, to the extent possible.

The site should manage any rash that occurs during the study according to the judgment of the investigator. Interventions may include supportive care, pharmacotherapy, laboratory evaluation, additional skin biopsies, and consultation with a dermatologist, as clinically indicated. Data from these additional interventions should be provided to the sponsor as part of the AE reporting after being deidentified and summarized by the investigative site.

8.4.7. Safety Monitoring

Lilly will periodically review evolving aggregate safety data within the study by appropriate methods.

Lilly will review SAEs within time frames mandated by company procedures. The Lilly medical monitor or designee will, as is appropriate, consult with the functionally independent Global Patient Safety medical physician or clinical scientist and periodically review the following in a blinded fashion:

- trends in safety data
- laboratory analytes
- AEs (including AESIs)

If a study subject experiences elevated ALT $\geq 3 \times$ ULN or elevated total bilirubin level $\geq 2 \times$ ULN, clinical and laboratory monitoring should be initiated by the investigator. Details for hepatic monitoring depend upon the severity and persistence of observed laboratory test abnormalities. To ensure subject safety and comply with regulatory guidance, the investigator is to consult with the Lilly medical monitor regarding collection of specific recommended clinical information and follow-up laboratory tests ([Appendix 4](#)).

In addition to the safety reviews performed by the blinded Study JPDA team mentioned above, the Assessment Committee will review the safety data in an unblinded fashion during the study and will determine whether dose reductions to any study arm should be made, and whether enrollment of Part B may proceed after review of Part A data. The Assessment Committee reviewing the safety data will include, at a minimum, a Lilly medical physician, a statistician, and a representative from Global Patient Safety; it will not include any Lilly study team members.

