- parenteral corticosteroids within 28 days prior to baseline or planned treatment during the study. (A single intra-articular corticosteroid injection is permitted within 28 days prior to baseline if no more than 40 mg triamcinolone [or equivalent] is administered and no further injections are planned during the study. The treated joint should be excluded from any joint-specific evaluations during the study.)
- prescription for oral prednisone (or equivalent) >10 mg/day or UNSTABLE PRESCRIBED DOSE within 28 days prior to baseline
- a chronic narcotic drug at an UNSTABLE PRESCRIBED DOSE within 28 days prior to baseline or planned increase/new prescription during the study
- gemfibrozil (a strong cytochrome P450 2C8 inhibitor) or alfentanil, dihydroergotamine, dofetilide, ergotamine, fentanyl, pimozone, or quinidine

(sensitive narrow therapeutic index cytochrome P450 3A substrates) within 28 days prior to baseline or planned treatment during the study

[15] have any clinically significant hematological or chemistry abnormalities at screening, including

- hemoglobin level <8.5 g/dL (<85 g/L)
- total platelet count <100 × 10⁹/L (<100 × 10³/μL or <100 Gi/L)
- total white blood cell count <3.0 × 10⁹/L (<3.0 × 10³/μL or <3.0 Gi/L)
- aspartate aminotransferase (AST) level >2.5 × ULN
- alanine aminotransferase (ALT) level >2.5 × ULN
- creatinine level ≥1.5 mg/dL (≥129 μmol/L)
- amylase >1.5 x ULN
- lipase >1.5 x ULN

A single repeat analysis is allowed according to investigator judgment prior to making a final determination of eligibility. The repeat laboratory test does not require a re-consent because the result does not constitute a screening failure until the clinically significant, out-of-range value is confirmed.

[16] have known hypogammaglobulinemia or a screening serum IgG level <565 mg/dL (<5.65 g/L)

A single repeat analysis is allowed according to investigator judgment prior to making a final determination of eligibility. The repeat laboratory test does not require a re-consent because the result does not constitute a screening failure until the clinically significant out-of-range value is confirmed.

[17] have evidence of or test positive for hepatitis C virus (HCV) at screening (defined as a positive test result for hepatitis C antibody [anti-HCVAb] plus a positive confirmatory test result for HCV [eg, HCV RNA])

Subjects whose results are anti-HCVAb positive and HCV RNA negative can be enrolled in the study, according to investigator judgment.

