7.1.2. Permanent Discontinuation from Study Drug

Discontinuation of the study drug for abnormal liver test results **should be considered** by the investigator (in consultation with the Lilly designated medical monitor) when a subject meets any of the following conditions:

- ALT or AST $>8 \times$ ULN
- ALT or AST $>5 \times$ ULN for more than 2 weeks
- ALT or AST $>3 \times$ ULN and either total bilirubin level $>2 \times$ ULN or international normalized ratio >1.5
- ALT or AST $>3 \times$ ULN with the appearance of fatigue, nausea, vomiting, right upper-quadrant pain or tenderness, fever, rash, and/or eosinophilia ($>5\%$)

In addition, immediate and permanent discontinuation of study drug should be considered for all subjects after the development of a rash (an AESI) deemed clinically significant by the investigator. See Section 8.4.6 for details on the assessment and management of subjects developing a rash.

The reason for and date of discontinuation from study drug will be collected for all randomized subjects. Subjects who discontinue study drug should also be discontinued from the study according to Section 7.1.4. All subjects who discontinue study drug early will have end-of-therapy procedures performed as shown for the early discontinuation visit (EDV) in the Schedule of Activities (Appendix 2).

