8.2. Adverse Events

Investigators are responsible for monitoring the safety of subjects who have entered this study and for alerting Lilly or its designee to any event that seems unusual, even if this event may be considered an unanticipated benefit to the subject.

The investigator is responsible for the appropriate medical care of subjects during the study.

Investigators must document their review of each laboratory safety report.

The investigator remains responsible for following, through an appropriate health care option, AEs that are serious or otherwise medically important, considered related to the study drug or the study, or that caused the subject to discontinue the study drug before completing the study. The subject should be followed until the event resolves, stabilizes with appropriate diagnostic evaluation, or is reasonably explained. The frequency of follow-up evaluations of the AE is left to the discretion of the investigator.

Lack of drug effect is not an AE in this study because the purpose of the clinical study is to establish treatment effect.

After the ICF is signed, study site personnel will record via the eCRF the occurrence and nature of each subject's pre-existing conditions, including clinically significant signs and symptoms of the disease under treatment in the study. In addition, site personnel will record via the eCRF any change in the condition(s) and any new conditions as AEs. Investigators should record their assessment of the potential relatedness of each AE to protocol procedure or study drug, via the eCRF.

The investigator decides whether he or she interprets the observed AEs as reasonably possibly related to RA, study drug, study procedure, or other concomitant treatment or pathology. To assess the relationship of the AEs, the following is defined:

reasonably possibly related: reasonable and temporal possibility that there is a cause and effect relationship between the study drug and/or study procedure and the AE

The investigator answers yes/no when making this assessment.

Adverse events will be graded for severity as mild, moderate, or severe, except for rashes (AESIs), which will be graded according to the Common Terminology Criteria for Adverse Events.

Planned nonsurgical interventions should not be reported as AEs unless the underlying medical condition has worsened during the course of the study.

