	Screening	Baseline (Randomi- zation)	Dosing Period				Safety Follow -Up	Additional HBV DNA Monitoring		Comments
			V101	V102	V103	V104		V105	V106 & EDV	
eCRF Visit Number (V)	V101	V102	V103	V104	V105	V106 & EDV	V802 ^a	V803 ^b	V804 ^b	
Study Day (±day(s))	≤28 Days from V2	1	15 ±2	29 ±2	57 ±3	85 ±3	99 +7	169 ±7	253 ±7	
Study Week		0	2	4	8	12	14	24	36	
HBV DNA (HBcAb+ subjects only)	X			X	X	X		X	X	Subjects who are HBcAb+ at screening, regardless of HBsAb status, will have an HBV DNA obtained by the central laboratory. Subjects who are found to be HBV DNA positive (detectable) at screening will be excluded from the trial. Subjects who are HBV DNA negative (undetectable) may be enrolled into the study with continued HBV DNA monitoring during the dosing period and every 3 months (for 6 months) after the last dose of study drug (refer to Section 8.4.7.1 for further details).
Lipid panel (nonfasting)		X				X				
TSH	X									
Serum chemistry	X	X	X	X	X	X	X			
Creatine kinase	X									
Hematology	X	X	X	X	X	X	X			
Hemoglobin A1C	X	X		X	X	X				
Urinalysis	X	X				X				
hsCRP	X	X	X	X	X	X				
Total Ig and Ig classes (IgG, IgA and IgM)	X					X				

Schedule of Activities, Protocol I8K-MC-JPDA – Part B

eCRF Visit Number (V)	Screening	Baseline (Randomization)	Dosing Period				Safety Follow-Up	Additional HBV DNA Monitoring		Comments
	V101	V102	V103	V104	V105	V106 & EDV	V802 ^a	V803 ^b	V804 ^b	
Study Day (\pm day(s))	≤ 28 Days from V2	1	15 ± 2	29 ± 2	57 ± 3	85 ± 3	99 +7	169 ± 7	253 ± 7	
Study Week		0	2	4	8	12	14	24	36	
RF and ACPA	X					X				ACPA may be reported by central laboratory as CCP.
Flow cytometry: lymphocyte subset samples (T cells and B cells)		X	X	X	X	X				
BTK-occupancy samples		X	X	X	X	X				Samples will be drawn only at sites that meet assay requirements.
pBTK samples		X	X	X	X	X				Samples will be drawn only at sites that meet assay requirements.
LY pharmacokinetics samples		X	X	X	X	X				At Visit 102, this sample should be collected 0.5-2 hours postdose.
Exploratory storage samples		X		X	X	X				
Pharmacogenetic sample		X								May be drawn at any time during the study if not drawn at Visit 102.
Clinical Measures										
Physician's Global Assessment of Disease Activity (VAS)		X	X	X	X	X				
Tender/swollen joint count	X	X	X	X	X	X				

Schedule of Activities, Protocol I8K-MC-JPDA – Part B

eCRF Visit Number (V)	Screening	Baseline (Randomization)	Dosing Period				Safety Follow-Up	Additional HBV DNA Monitoring		Comments

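### Protocol 8.4.7 starts early liver monitoring on ALT or bilirubin but not AST, although every liver stopping condition in 7.1.2 counts either enzyme; add AST to the trigger

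*Protocol*

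**What the plan says.** **Early step.** Protocol 8.4.7 has two triggers, ALT ≥3 × ULN or total bilirubin ≥2 × ULN, introduced by "If a study subject experiences elevated ALT". Either one starts clinical and laboratory monitoring, and the investigator then consults the sponsor's medical monitor about follow-up tests. No repeat interval is fixed: "Details for hepatic monitoring depend upon the severity and persistence of observed laboratory test abnormalities".

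**Later step.** Protocol 7.1.2 asks the investigator to consider stopping study drug, "in consultation with the Lilly designated medical monitor", when ALT or AST is:

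1. above 8 × ULN;
2. above 5 × "ULN for more than 2 weeks";
3. above 3 × ULN with bilirubin above 2 × ULN or INR above 1.5; or
4. above 3 × ULN with any of a list of symptoms and signs, including rash and eosinophilia.

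**AST elsewhere.** Exclusion criterion [15] sets the same 2.5 × ULN limit for ALT and for "aspartate aminotransferase (AST) level". AST belongs to the chemistry panel in Appendix 3, and the Appendix 2 row "Serum chemistry" is marked at every dosing-period visit. SAP 6.4.5.1 lists AST and ALT at the same multiples of 3, 5 and 10.

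**General follow-up.** Under Protocol 8.4.5, "Any clinically significant findings that occur after the subject receives the first dose of study drug should be reported to Lilly" or its designee as adverse events. Protocol 8.2 requires review of each laboratory safety report and follow-up of medically important events, but "The frequency of follow-up evaluations of the AE is left to the discretion of the investigator".

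**The concern.** The early step produces the information on which the later decision depends. For ALT, the protocol tells the investigator at 3 × ULN to start looking and to talk to the medical monitor. For AST at the same level with nothing else abnormal, it gives no such direction, yet 7.1.2 later gives AST the same weight as ALT. No other section supplies an AST threshold for early monitoring or explains why AST was left out.

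What is at stake is timely recognition of a possible liver signal in individual subjects. Two 7.1.2 conditions need information that routine visits may not give in time: an INR, and a repeat value showing that the rise has lasted more than 2 weeks.

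**Working it through.** There is no sample-size or error-rate figure to reproduce. The check sets the provisions side by side.

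**Count.** AST appears in 4 of the 4 conditions in 7.1.2 and in 0 of the 2 limbs of the 8.4.7 trigger.

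**What an isolated AST rise meets.** Take ALT <3 × ULN, bilirubin <2 × ULN and none of the condition 4 symptoms or signs, with INR not yet known.

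| AST (× ULN) | 8.4.7 trigger | 7.1.2 condition | Same value in ALT |
|---|---|---|---|
| 3 to 5 | not met | none, unless AST is above 3 and INR is found above 1.5 (condition 3) | 8.4.7 met |
| above 5, up to 8 | not met | condition 2 after more than 2 weeks, or condition 3 if INR is above 1.5 | 8.4.7 met |
| above 8 | not met | condition 1 at once, with consultation | 8.4.7 met |

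The gap is thus a missing early step for AST between 3 and 8 × ULN. The bilirubin limb of condition 3 is not part of it, because bilirubin above 2 × ULN trips 8.4.7 by itself. Condition 4 is not part of it either, because the symptoms or signs bring the subject directly under 7.1.2.

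**INR.** It is absent from the routine tests in Appendix 3. It appears among the hepatic follow-up tests in Appendix 4, which may be obtained and may be requested after consultation with the medical monitor. For isolated AST, nothing directs that consultation.

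**Persistence.** Part B dosing visits are at Days 1, 15, 29, 57 and 85. The first two intervals are nominally 15 − 1 = 14 and 29 − 15 = 14 days. The next two are 57 − 29 = 28 and 85 − 57 = 28 days. A value above 5 × ULN first seen at Day 29 or Day 57 therefore needs an unscheduled retest if persistence is to be judged soon after 2 weeks. For ALT, 8.4.7 prompts the investigator to act; for AST it does not.

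**What still catches AST.**

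- Chemistry is measured at every dosing-period visit and at the safety follow-up visit.
- The medical monitor periodically reviews laboratory analytes, blinded (8.4.7).
- The Assessment Committee reviews safety data, unblinded (8.4.7).
- Unscheduled chemistry is allowed at the investigator's discretion (Appendix 3, note c).
- Appendix 4 covers any treatment-emergent hepatic abnormality, not only ALT.
- Adverse-event follow-up applies (8.2, 8.4.5).

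Each of these is periodic or discretionary, or merely supplies the value. None sets an AST level at which the investigator is told to act.

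**The case against.** The strongest reply is that a monitoring trigger and a discontinuation list serve different purposes and need not use the same analytes. AST is less specific to the liver, so an ALT-only trigger could be deliberate. The hepatic lists differ in other ways too: exclusion [15] has no bilirubin limit although bilirubin triggers 8.4.7, and the SAP lists alkaline phosphatase, which neither 8.4.7 nor 7.1.2 uses. Protocol 4.5 describes gastrointestinal, pancreatic, immune and skin effects and no hepatic signal.

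Much of this stands. The pairing of AST with ALT at entry and in the SAP listing is only supporting evidence; the latter is a reporting output. The comparison that carries weight is between 8.4.7 and 7.1.2, because one step feeds the other. If ALT-only is intended, the protocol does not say so.

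Four stronger readings are tempting but not supported:

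- *Isolated AST rises go without follow-up.* They do not, given the safeguards listed above.
- *AST from 3 to 8 × ULN lies wholly outside 7.1.2.* It does not: condition 2 applies above 5 × ULN once the rise has lasted more than 2 weeks, and condition 3 applies above 3 × ULN if INR exceeds 1.5.
- *The 28-day visit gaps measure the harm.* They come from the calendar and apply equally to ALT if nobody acts. Since 8.4.7 fixes no repeat interval, adding AST would prompt action but would not guarantee a shorter interval.
- *A stopping rule is missed, or guidance is breached.* 7.1.2 is advisory. 8.4.7 refers to regulatory guidance, but the documents do not reproduce it, so compliance cannot be judged from them.

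**Conclusion.** The point holds as a minor one. Protocol 8.4.7 omits AST from the early trigger although 7.1.2 counts AST in every condition, which leaves isolated AST rises between 3 and 8 × ULN without a directed early step. The practical effect is that the INR and the retest that conditions 3 and 2 may need are not prompted.

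This rests on reading 8.4.7 as written, with no AST trigger in any other section. It assumes no event rate: the documents give no frequency for isolated AST rises, so the number of subjects affected cannot be estimated. The ACR20 analysis, power and alpha are unaffected.

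**What to change.** Change the 8.4.7 trigger to ALT or AST ≥3 × ULN, or total bilirubin ≥2 × ULN. If an ALT-only trigger is intended, state that in 8.4.7 with the reason.

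The cost is two added words and a few extra consultations and liver panels, in subjects who already have an abnormal value. Some of those AST rises will not be hepatic; creatine kinase is already in the Appendix 4 panel and helps to sort them.

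A separate, optional improvement for both enzymes would be to direct a repeat just after 14 days when a value exceeds 5 × ULN, and an INR when it exceeds 3 × ULN. That, rather than the added AST trigger, would secure the timing of the persistence check.
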